		
has resumed and questioned about factors that may affect resumption of menses.
 
 Patients with endometrial biopsy findings of endometrial hyperplasia or endometrial cancer on the endometrial biopsy at the Week 24/Early Termination visit will undergo a repeat biopsy in 3 to 6 months after the Week 24/Early Termination and will be contacted to obtain information on procedures performed or treatments received (if any) for the biopsy findings during through the time of the repeat biopsy. The repeat biopsy will be submitted to the central laboratory. In addition, patients with endometrial hyperplasia with atypia will be evaluated and managed, as needed, by a gynecologist. Patients who have had a bone mineral density loss of > 2% at the lumbar spine (average of L1-L4) or total hip at their Week 24/Early Termination visit relative to baseline will undergo a follow-up DXA scan 6 months (\pm 1 month) after discontinuation of study drug and will be contacted to obtain information about medications and conditions (eg, pregnancy, hyperparathyroidism, hypothyroidism, etc) that might affect bone mineral density through the time of the repeat DXA scanning. The follow-up DXA scan will be submitted for central reading. 	
Section 6.8.1.2 Transvaginal and Transabdominal Ultrasound	None.	Saline or gel contrast is not required, but may be performed to demonstrate fibroids that meet the criterion for inclusion if these are not adequately visualized with transvaginal ultrasound alone or when endometrium cannot be evaluated or when	Added clarification regarding use of saline or gel contrast for ultrasound.

Item; Section(s)	Protocol Amendment 1	Amendment 2	Rationale
		there are ambiguous and potentially exclusionary findings on the transvaginal or transabdominal ultrasound (eg, suspected intrauterine masses, equivocal endometrial findings, etc.). If transabdominal ultrasound or ultrasound with saline or gel contrast is performed at Screening, it should also be performed at Week 24	
Section 6.8.1.5 Patient Diary	The eDiary data will be reviewed by the investigator to identify any potential adverse events.	The eDiary data will be reviewed by the study staff . investigator to identify any potential adverse events	To ensure consistency with section 7.2 of the protocol stating that eDiary entries will be reviewed by study site personnel.
Section 6.8.1.9 Patient Global Assessment for Symptoms and Patient Global Assessment for Function	None.	These simple questions are used by the patient to qualitatively describe severity of symptoms or effects on function (PGA) (see Appendix 6) on a schedule described in the Schedule of Activities (Section 1.1). With the exception of Baseline Day 1 (see Section 1.1), patients will answer these questions before other types of study procedures. The PGA for function and PGA for symptoms will be completed on a paper questionnaire at the study site on a schedule described in the Schedule of Activities (Section 1.1). With the exception of Baseline Day 1, patients will answer these questions before other types of study procedures. The PGA for function and PGA for symptoms will be completed on a paper questionnaire at the study site.	New section added to describe assessments for the newly add PGA secondary objectives.

Item; Section(s)	Protocol Amendment 1	Amendment 2	Rationale
Section 6.8.1.10 Status of Menstruation Recovery	After the Follow-up visit, additional follow-up for the status of menstruation recovery will not be continued.	None.	Menstruation recovery follow up outlined in Section 6.6.
Section 6.8.2.3 Physical and Gynecologic Exams	Visual acuity will be checked at the beginning and end of the study by a standard visual eye chart. The patient should wear any prescribed glasses or contacts during the visual acuity assessment.	None.	Visual acuity assessment instructions moved to a new section.
Section 6.8.2.4 Clinical Laboratory Samples Table 6-1	Chemistry Creatinine Kinase Hormones Intact Parathyroid Hormone	Chemistry Creatinine Kinase Hormones Intact Parathyroid Hormone	Parathyroid hormone testing is removed (patients with abnormal calcium and phosphorus will be excluded). “Creatinine kinase” Typographical error removed.
Section 6.8.2.6 Endometrial Biopsy	An endometrial biopsy is to be performed during the pelvic examination at the Screening 3 visit. A pipelle should be used to obtain the specimen. A second biopsy is to be performed at the Week 24 visit. The biopsies will be read centrally.	An endometrial biopsy will be obtained using an endometrial suction curette (eg, Pipelle®) and submitted to the central laboratory for reading. If the biopsy is inadequate for diagnosis at either Screening or at Week 24, it should be repeated and sample submitted to the central laboratory. If the second specimen is also inadequate for diagnosis at Screening, the patient is not eligible for the study.	To provide clarification and details for endometrial biopsy.
Section 6.8.2.7 Bone Mineral Density	Bone mineral density is determined using DXA scanning and will be assessed at the lumbar spine (L1, L2, L3 and L4), total hip, and femoral neck (same leg within each patient).	Bone mineral density is determined using DXA scanning and will be assessed at the lumbar spine (L1, L2, L3 and L4), total hip, and femoral neck (same leg within each patient). The scans will be read by the central radiology laboratory in accordance with the imaging charter.	Added clarification of central reading.
Section 6.8.2.7 Bone Mineral Density	The following will be assessed at each time point indicated for bone densitometry in the study Schedule of Activities (Section	None.	Deleted details on analysis of bone mineral density. This info will be

Item; Section(s)	Protocol Amendment 1	Amendment 2	Rationale
	1.1): bone mineral content (g), bone area (area, cm ²), and bone mineral density (g/cm ²) each for L1, L2, L3, L4, total hip, and femoral neck, average bone mineral density of L1-L4, and T-score for average of L1-L4, total hip, and femoral neck.		provided in the SAP.
Section 6.8.2.7 Bone Mineral Density	
Investigators will be notified if a patient experiences a bone mineral density loss from baseline of 7% or more at any of the sites assessed during the study. In this case, repeat scan may be required for confirmation of the results, and it is at the investigator's discretion to consider the patient's status and determine future management. Detailed instructions for bone mineral density monitoring will be provided in the Study Reference Manual.
	
Investigators will be notified if a patient experiences a bone mineral density loss from baseline of 7% or more at any of the anatomical sites assessed during the study. In this case, repeat scan may be required for confirmation of the results, and it is at the investigator's discretion to consider the patient's status and determine future management. Detailed instructions for bone mineral density monitoring DXA scanning will be provided in the Study Reference Manual.
 
Please see Section 6.6 for follow-up of patients who are not continuing into the extension study (MVT-601-3003) and whose bone mineral density has decreased by > 2% at the lumbar spine (L1-L4) or total hip at the Week 24/Early Termination visit relative to Baseline.
	Further specified follow-up measures for observed bone mineral density loss.
Section 6.8.2.8 Visual Acuity	None.	Presenting visual acuity must be assessed with the supplied study eye chart. If the patient uses corrective lenses, she should wear her usual prescription glasses or contact lenses during the assessment, and the same prescription lenses should be worn at subsequent visual testing, as possible. Perform the visual acuity testing using the entire eye chart. Do not stop at a visual acuity of 100 – continue as far as the patient can go per the testing instructions (see Study Reference Manual for additional details).	New section created to provide additional details and to align with other studies with relugolix.

Item; Section(s)	Protocol Amendment 1	Amendment 2	Rationale
		
Patients whose presenting visual acuity score is 90 or lower at the Baseline visit should be encouraged to obtain a diagnostic evaluation from an eye care provider, ie, an ophthalmologist or an optometrist. Any findings (ie, diagnoses) from the eye examination should be recorded as medical history.
 
Patients whose presenting visual acuity score at Week 24 /Early termination has decreased by 10 or more points from Baseline should be referred to an ophthalmologist for a diagnostic evaluation. A copy of the ophthalmology consultation must be submitted to the sponsor.
	
Section 7.1.1 Adverse Event	
Events that do not meet the definition of an adverse event include:
 
...
 
 • None. 	
Events that do not meet the definition of an adverse event include:
 
...
 
 • Events of heavy menstrual bleeding, as heavy menstrual bleeding is quantified as an efficacy endpoint, unless the event meets seriousness criteria. 	As heavy menstrual bleeding is being assessed as an efficacy endpoint, added it to list of events that do not meet definition of adverse event. Also clarified that would be reportable as an adverse event if met the criteria for seriousness.
Section 7.6 Serious Adverse Event Reporting	Table providing details to send completed Safety Report Forms to PRA Safety & Risk Management	Table updated to send completed Safety Report Forms to QuintilesIMS	Updated Contact info for reporting Serious Adverse events. Updates to e-mail and phone number are also included in this section.
Section 7.10 Benefit/Risk Assessment Table 7-2	
Impact on Eligibility
 
Exclusion criteria for a history of osteoporosis, osteopenia, metabolic bone disease, ...
	
Impact on Eligibility
 
Exclusion criteria for a history of osteoporosis, osteopenia, metabolic bone disease, ...
	Osteopenia is not an exclusion criterion in this study.
Section 7.10 Benefit/Risk Assessment Table 7-2	Hepatic Enzymes	Hepatic Enzyme Increase	Updated naming of this potential risk, matching IB nomenclature

Item; Section(s)	Protocol Amendment 1	Amendment 2	Rationale
Section 9.2 Statistical Considerations and Data Analyses	The Per-Protocol Population will consist of those members of the ITT Population who have no major protocol violations.	The Per-Protocol Population will consist of those members of the ITT Population who have no relevant major protocol violations, defined as a subset of all major protocol violations (details will be provided in the statistical analysis plan).	Clarification.
Section 9.3.2 Statistical Considerations and Data Analyses	
For the secondary endpoints of time to achieving a menstrual blood loss volume of < 80 mL AND at least a 50% reduction from baseline menstrual blood loss volume and time to amenorrhea, time to event will be defined as weeks from randomization to first occurrence of the event as assessed by the alkaline hematin method.
 
Patients for whom the first time at which menstrual blood loss of <80 mL AND at least a 50% reduction from baseline is achieved is during a cycle when no feminine products were returned due to amenorrhea absence of a menstrual period, the most recent menstruation stop date will be used.
 
...
 
Descriptive statistics will be provided for changes in menstrual blood loss, hemoglobin, Numerical Rating Scale score for uterine fibroid-associated pain, uterine volume, and uterine fibroid volume baseline.
	
For the secondary endpoints of time to achieving a menstrual blood loss volume of < 80 mL AND at least a 50% reduction from baseline menstrual blood loss volume and time to amenorrhea, time to event will be defined as weeks from randomization to first occurrence of the event as assessed by the alkaline hematin method.
 
Patients for whom the first time at which menstrual blood loss of <80 mL AND at least a 50% reduction from baseline is achieved is during a cycle when no feminine products were returned due to amenorrhea absence of a menstrual period, the most recent menstruation stop date will be used.
 
...
 
Descriptive statistics will be provided for changes in menstrual blood loss, hemoglobin, UFS-QOL score, PGA for function and symptoms, MIQ Score, Numerical Rating Scale score for uterine fibroid-associated pain, uterine volume, and uterine fibroid volume baseline.
	Changes made to ensure consistency with changes in secondary efficacy endpoints.
Section 9.4 Safety Analyses	None.	To support the inclusion of add-back therapy in the treatment regimen, the safety endpoint of mean percent change from Baseline in bone mineral density lumbar spine at Week 12 will be analyzed using pooled data from the two replicate studies (MVT-601-3001 and MVT-601-3002) with a formal comparison of	To provide clarification on analysis plans for bone mineral density which includes pooling of data across the two replicate studies.

Item; Section(s)	Protocol Amendment 1	Amendment 2	Rationale
		Group A versus Group B (see details in the joint statistical analysis plan).	
Appendix 6 Patient Global Assessments	None.	
Patient Global Assessment (for function)
 
How much were your usual activities limited by uterine fibroids symptoms such as heavy bleeding over the last 4 weeks?
 
 1. No limitation at all 2. Mild limitation 3. Moderate limitation 4. Quite a bit of limitation 5. Extreme limitation 
Patient Global Assessment (for symptoms)
 
How severe were your uterine fibroids symptoms such as heavy bleeding over the last 4 weeks?
 
 1. Not severe 2. Mildly severe 3. Moderately severe 4. Very severe 5. Extremely severe 	To support secondary objectives.

CLINICAL STUDY PROTOCOL

Study Title:	LIBERTY 1: An International Phase 3 Randomized, Double-Blind, Placebo-Controlled Efficacy and Safety Study to Evaluate Relugolix Co-Administered with and without Low-Dose Estradiol and Norethindrone Acetate in Women with Heavy Menstrual Bleeding Associated with Uterine Fibroids
Investigational Product:	Relugolix
Protocol Number:	MVT-601-3001
Indication:	Treatment of heavy menstrual bleeding associated with uterine fibroids
Sponsor:	Myovant Sciences GmbH [name] Switzerland
Regulatory Identifier(s):	EudraCT # 2016-003727-27 IND # 131161
Version and Effective Date:	Original: 10-NOV-2016 Amendment 1: 08-FEB-2017 Amendment 2: 18-SEP-2017

CONFIDENTIALITY STATEMENT

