- d. The Baseline Day 1 visit should occur within 7 days of the onset of menses. The following procedures must be completed prior to randomization: urine pregnancy, vital signs, waist circumference, weight, temperature, complete physical examination, visual acuity assessment, 12-lead ECG, and review of eligibility criteria. Collect clinical laboratory sample, PK sample, pharmacodynamic sample, and urinalysis prior to first dose of study drug. Whenever possible, complete MIQ, UFS-QOL, PGA for symptoms and PGA for function, and EQ-5D-5L prior to the first dose of study drug.
- e. For an Unscheduled visit, these procedures will be performed as needed, based on the reason(s) for the Unscheduled visit. The last dose of study drug in the Randomized Treatment Period will be taken on the day immediately before the Week 24 visit. Note: Week 24 visit is defined as the last day on which a Week 24 visit procedure is conducted.
- f. Follow-up visit: For women who do not continue into the open-label extension study (MVT-601-3003) and/or terminate early from the study, a follow-up visit to assess safety will be scheduled approximately 30 days after the last dose of study drug, or prior to the date of initiation of another investigational agent or hormonal therapy affecting the hypothalamic-pituitary-gonadal axis or surgical intervention for uterine fibroids, whichever occurs first (ie, ~Week 28 for patients who complete the study or ~30 days after an Early Termination visit).
- g. Collect serious adverse event information from the time of signed informed consent through approximately 30 days after the last dose of study drug, or the date of initiation of another investigational agent or hormonal therapy affecting the hypothalamic-pituitary-gonadal axis or surgical intervention for uterine fibroids, whichever occurs first. Collect nonserious adverse event information from the Baseline Day 1 visit (or from the time of signed informed consent if event was related to a screening study procedure) through approximately 30 days after the last dose of study drug, or the date of initiation of another investigational agent or hormonal therapy affecting the hypothalamic-pituitary-gonadal axis or surgical intervention for uterine fibroids, whichever occurs first.

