6.2.1. Screening 1 Visit

The Screening 1 visit will be conducted following the signing of the informed consent form and may occur at any time during the menstrual cycle. The Screening 1 visit will include a full medical history (including menstrual history for 3 months prior to Screening and prior uterine imaging assessments), review of inclusion and exclusion criteria, collection of concomitant medications, study procedure-related adverse events and any serious adverse events. In addition, vital signs, height, weight, temperature, a complete physical examination, visual acuity assessment, gynecology examination, ultrasound, endometrial biopsy, Papanicolaou test (if needed), clinical laboratory tests, urinalysis, and a urine pregnancy test will be done. Feminine products will be dispensed with instructions to collect and return all products used during the next menses. The paper diary will also be dispensed at this visit and should be completed daily starting with this visit. The bone mineral density scan and mammogram should be scheduled at this time (or within a few days of this visit). Bone densitometry should be scheduled to be prior to the Screening 3 visit and as early as feasible to ensure results are available prior to randomization.

The order of procedures should be as follows. Patients not meeting eligibility criteria after any procedure should not undergo subsequent procedures.

- Medical history and review of prior uterine imaging studies
- Review of concomitant medications (including supplements and over the counter medications)
- Review of inclusion and exclusion criteria
- Urine pregnancy test
- Vital signs, weight, and height
- Complete physical examination and visual acuity assessment
- Ultrasound – do not proceed with additional procedures if no uterine fibroids are identified with the local/initial reading
- Gynecology examination, Papanicolaou test (if need), endometrial biopsy, clinical laboratory tests, including TSH, urinalysis
- Dispense feminine products and paper diary with instructions to begin recording starting information daily, starting on the Screening 1 visit day
- Schedule mammogram (if needed)
- Schedule bone densitometry

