6.3. Randomized Treatment Period (Baseline to Week 24)

At the Baseline Day 1 visit, patients will be randomized to one of the three study treatment arms (see [Section 5.3](#)). Patients will take their randomized study treatment once daily, beginning on the day of the Baseline Day 1 visit and continuing through the Week 24 visit. Patients will continue recording daily in their eDiary. On-treatment study visits will occur every 4 weeks through the end of Week 24. At each post-baseline visit, patients will return their feminine products for alkaline hematin testing. Safety monitoring including signs and symptoms directed physical examination, waist circumference, ECGs, clinical laboratory tests, pregnancy tests, and adverse event collection will occur at each visit. Bone densitometry will occur at the Week 12

and Week 24 visits. A repeat transvaginal ultrasound (with or without a transabdominal ultrasound) and endometrial biopsy will be performed at the Week 24 visit. The endometrial biopsy will be read centrally. Study drug and eDiary compliance will be reviewed at each visit. Refer to the Schedule of Activities in the synopsis (see [Section 1.1](#)) for information about study procedures during the randomized treatment period.

Sites should try to schedule patient visits during the morning, instructing patients to arrive before taking their study drug to allow for pre-dose PK/pharmacodynamic sampling on visits at which these specimens are drawn. Patients must come to the clinic in the fasted state (eg, nothing to eat or drink other than water after midnight the day before the clinic visit) for the Baseline Day 1 and Week 24/Early Termination visits.

For visits *other than* Baseline Day 1 and Week 24/Early Termination, if the clinic visit cannot be scheduled for the morning, patients may eat in the morning but should not have eaten or had anything to drink other than water, coffee, or tea for at least 2 hours prior to the clinic visit and must not eat or drink (other than water, coffee or tea) for at least 1 hour after the clinic visit. In these situations, the laboratory requisitions must indicate that the patient was not fasted for their chemistry and lipid testing.

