6.8.2.8. Visual Acuity

Presenting visual acuity must be assessed with the supplied study eye chart. If the patient uses corrective lenses, she should wear her usual prescription glasses or contact lenses during the assessment, and the same prescription lenses should be worn at subsequent visual testing, as possible. Perform the visual acuity testing using the entire eye chart. Do not stop at a visual acuity of 100 – continue as far as the patient can go per the testing instructions (see Study Reference Manual for additional details).

Patients whose presenting visual acuity score is 90 or lower at the Baseline visit should be encouraged to obtain a diagnostic evaluation from an eye care provider, ie, an ophthalmologist or an optometrist. Any findings (ie, diagnoses) from the eye examination should be recorded as medical history.

Patients whose presenting visual acuity score at Week 24 /Early termination has decreased by 10 or more points from Baseline should be referred to an ophthalmologist for a diagnostic evaluation. A copy of the ophthalmology consultation must be submitted to the sponsor.

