7.1. Adverse Event Definitions

7.1.1. Adverse Event

Adverse event: An adverse event is any unfavorable and unintended sign (including an abnormal laboratory finding), symptom, or disease (new or exacerbated) temporally associated with the use of a medicinal product, whether or not related to the medicinal product.

Events meeting the definition of an adverse event **include**:

- A worsening, excluding minor fluctuations, in the nature, severity, frequency, or duration of a pre-existing condition;

- Development of an intercurrent illness during the study;
- Development of symptoms that may or may not be related to the use of a concomitant medication or investigational product;
- Injury or accidents: If a medical condition is known to have caused the injury or accident, the medical condition and the accident should be reported as 2 separate medical events (eg, for a fall secondary to dizziness, both “dizziness” and “fall” should be recorded separately); and
- An investigational abnormality (eg, laboratory parameter, vital sign, ECG) only if the abnormality is considered clinically significant by the investigator based on at least one of the following criteria:
 - Induces clinical signs or symptoms;
 - Requires active intervention;
 - Requires interruption or discontinuation of study drug.

Events that **do not** meet the definition of an adverse event include:

- Medical or surgical procedures (eg, surgery, endoscopy, tooth extraction, transfusion); the condition that leads to the procedure is an adverse event;
- Pre-existing diseases or conditions present or detected before the start of study drug administration that do not worsen;
- Situations where an untoward medical event has not occurred (eg, planned hospitalization for an elective procedure, with elective defined as known or planned at the time of signing of the informed consent).
- Events of heavy menstrual bleeding, as heavy menstrual bleeding is being quantitatively measured as an efficacy endpoint, unless the event meets seriousness criteria.

Adverse events that occur during the study should be evaluated by the investigator and graded according to Common Terminology Criteria for Adverse Events (CTCAE). Episodic adverse events, such as vomiting, or those that occur repeatedly over a period of consecutive days are ‘intermittent’. All other events are ‘continuous’. Additional information on detecting, documenting, and reporting adverse events and serious adverse events are provided below.

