7.2.1. Adverse Event Reporting Period

Adverse events will be collected from the time the first dose of study drug is administered until the Follow-up visit approximately 30 days after the last dose of study drug or the date of initiation of another investigational agent or hormonal therapy affecting the hypothalamic-pituitary-gonadal axis or surgical intervention for uterine fibroids, whichever occurs first, as also specified in the study Schedule of Activities ([Section 1.1](#)). Study procedure-related adverse events will be collected from the signing of the informed consent form.

Serious adverse events will be collected from the signing of the informed consent form until the safety follow-up visit approximately 30 days after the last dose of study drug. Serious adverse events reported to the investigator after the safety reporting period should be reported to the sponsor if the investigator assesses the event as related to the study drug treatment.

With the exception of adverse events that are considered related to study screening procedures, (which are to be recorded as adverse events), events occurring between signing of the informed consent form and the first dose of study drug will be recorded as medical history and in the patient's clinical record for any patient who continues to meet eligibility criteria and proceeds to dosing with study drug.

Reporting instructions for serious adverse events are provided in [Section 7.6](#).

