Hepatic Enzyme Increase Isolated increases in hepatic transaminases have been observed in prior clinical studies. There have been no reported cases consistent with drug-induced liver injury including an increase in bilirubin. Abnormal LFTs are considered adverse events of clinical interest in this study.	Exclusion criteria for AST and ALT > 2 x the ULN; total bilirubin values > 1.5 x ULN	Abnormal LFTs (AST or ALT > 3 x ULN) that develop during the randomized treatment period will be reported within 24 hours of study personnel awareness.
Phospholipidosis Data from nonclinical studies in rats and monkeys showed histopathological changes consistent with PLD. PLD by itself is not adverse. No clinical evidence of relugolix-related PLD-associated toxicity has been observed nor was there a clinically meaningful increase in a biomarker of PLD assessed in phase 2 clinical studies.	Patients with significant underlying medical conditions are excluded.	Routine safety monitoring including laboratory assessments, ECGs, and assessment of adverse events; visual acuity will be checked at the beginning and end of the study.
Metabolic Changes Metabolic changes (insulin resistance, dyslipidemia, and increased weight) with increased risk of diabetes are a potential risk of the hypoestrogenic state induced by relugolix.	Exclusion criteria for current medical history of cardiovascular disease.	Fasting lipids and glucose will be monitored during the study.
Reproductive Toxicity	Premenopausal compliance with specified acceptable non-hormonal contraception; exclusion of pregnant and lactating women.	Monthly pregnancy testing; immediate withdrawal for pregnancy.
Risk of Estradiol (1.0 mg)/Norethindrone Acetate (0.5 mg) Low-dose estradiol and norethindrone acetate are approved for the prevention of postmenopausal osteoporosis and the treatment of moderate to severe vasomotor symptoms. It is contraindicated for women with a history of breast cancer or	Women with breast cancer or other estrogen-dependent malignances, a history of deep vein thrombosis, pulmonary embolism, thromboembolic disease, liver dysfunction, prior	Clinical chemistries assessing LFTs, fasting glucose and lipids, and urine pregnancy tests will be performed throughout the study. Adverse events will be recorded at each visit.

Potential Risk of Clinical Significance	Mitigation Strategy	
	Impact on Eligibility	Monitoring and Withdrawal Criteria

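### Section 6.8.2.8 files every diagnosis from the Baseline-prompted eye examination as medical history, with no condition on onset or worsening, so a condition that begins or worsens after the first dose and is first diagnosed there would be misfiled

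*Protocol*

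**What the plan says.** Section 6.8.2.8 sets the trigger: "Patients whose presenting visual acuity score is 90 or lower at the Baseline visit should be encouraged to obtain a diagnostic evaluation". The evaluation is done by an ophthalmologist or optometrist, and no date is set for it. The recording rule follows: "Any findings (ie, diagnoses) from the eye examination should be recorded as medical history". The Amendment 2 summary of changes carries the same wording, so this is current text.

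On timing, footnote d of the Schedule of Activities says of Baseline Day 1: "The following procedures must be completed prior to randomization: urine pregnancy, vital signs, waist circumference, weight, temperature, complete physical examination, visual acuity assessment". Section 6.3 adds: "Patients will take their randomized study treatment once daily, beginning on the day of the Baseline Day 1 visit".

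On adverse events, Section 7.2.1 says: "Adverse events will be collected from the time the first dose of study drug is administered until the Follow-up visit". The same section sends to medical history what occurs between consent and first dose, apart from events related to screening procedures. Section 7.1.1 counts new or exacerbated disease as an adverse event. The relevant item it exempts is: "Pre-existing diseases or conditions present or detected before the start of study drug administration that do not worsen".

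**The concern.** The rule in 6.8.2.8 classifies a finding by the examination that produced it. The adverse event sections classify it by when it began and whether it worsened. The two agree for a long-standing condition that explains a low score on Day 1. They disagree for a condition that starts or progresses on study drug and first comes to light at that examination. A site cannot then satisfy both: following 6.8.2.8 to the letter breaches 7.1.1 and 7.2.1, and the reverse also holds.

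Treatment-emergent adverse events are a safety endpoint. Table 7-2 also names acuity among the monitoring items for phospholipidosis: "visual acuity will be checked at the beginning and end of the study". Any misfiling runs in one direction, because it takes events out of the adverse event tables and never adds any.

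**Working it through.** The main check is textual. The protocol states no figure on this point that could be reproduced.

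**1. When the examination takes place.** Table 1-1 marks acuity at Baseline Day 1 and at Week 24/Early Termination, and as needed at unscheduled visits. Footnote d puts the Day 1 test before randomization, and Section 6.3 starts dosing that day. Nothing holds dosing until the eye examination is done, and no deadline is given. An outside appointment prompted by that day's score will therefore ordinarily fall after the first dose, inside the adverse event collection window. The protocol does not say this outright.

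**2. How a finding is classified.**

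| Finding at that examination | Section 6.8.2.8 | Sections 7.1.1 and 7.2.1 | Agree? |
|---|---|---|---|
| Present before first dose, not worsened | Medical history | Exempt from adverse event definition | Yes |
| Present before first dose, worsened since | Medical history | Adverse event | No |
| Began after first dose | Medical history | Adverse event | No |

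A late date of diagnosis does not by itself create a conflict. Section 7.1.1 exempts conditions present or detected before dosing, so presence is enough. The conflict is confined to the last two rows.

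**3. What else would catch such a case.** Adverse events are collected at every visit (Table 1-1), and Section 7.2 requires all of them to be documented. Every woman's acuity is retested at Week 24/Early Termination. A fall of 10 or more points leads to ophthalmology referral, with the report sent to the sponsor. The medical-history sentence comes before that paragraph and is not repeated in it. These routes have limits: no acuity test is scheduled between Day 1 and Week 24/Early Termination, a smaller fall triggers no referral, and no copy of the Baseline-prompted examination has to go to the sponsor.

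**4. Size, for illustration only.** The protocol gives no share of women scoring 90 or lower, no attendance rate, no examination date and no ocular event rate. Suppose 10% to 30% score 90 or lower, all of them attend, and true on-treatment ocular incidence is 2%. These rates are assumptions without a source.

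- Relugolix women: 2 × 130 = 260. Under the rule: 260 × 0.10 = 26 to 260 × 0.30 = 78.
- Events in 260 women: 260 × 0.02 = 5.2.
- If every event in the affected women is first found at that examination: 5.2 × 0.10 = 0.5 to 5.2 × 0.30 = 1.6. This is a ceiling under these rates.
- If events are uniform over 24 weeks and the examination falls at Week 4, only 4/24 of them can precede it: 0.52 × 4/24 = 0.09 to 1.56 × 4/24 = 0.26.

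The result depends almost entirely on the assumptions. It shows only that the count is small under each set tried.

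**The case against.** A reader might infer that eye disease arising on treatment goes unrecorded as an adverse event in women with low Baseline acuity. The protocol does not support that. The sentence covers findings from one examination only, and nothing in 6.8.2.8 suspends the general adverse event rules. Questioning at visits and the Week 24/Early Termination retest apply to these women as to all others. Section 4.6 also lists a clinically significant decrease in acuity, as evaluated by an ophthalmologist, among the reasons for removal from therapy.

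The rule also has a sensible purpose. The deficit that prompts the examination was measured before randomization, so a diagnosis that explains it is pre-existing whenever it is named. The stakes should not be inflated either: the protocol reports no damage to eye structure or function in the 4- and 39-week monkey studies, and acuity is one of several monitoring items for phospholipidosis.

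All of this stands, and it narrows the point. What it does not remove is the word covering any finding, with no onset qualifier. A site given a specific instruction for a specific examination would reasonably follow it over the general rule.

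**Conclusion.** The point holds as a minor correction. The sentence in 6.8.2.8 conflicts with 7.1.1 and 7.2.1 for one narrow class: an eye condition that begins or worsens after the first dose and is first diagnosed at the Baseline-prompted examination. This rests on two things: a literal reading of the sentence, and the inference that the examination ordinarily follows the first dose. The number of women affected cannot be estimated from the protocol and is probably very small.

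There is also a separate inconsistency. Section 6.2.1 lists this among the Screening 1 procedures: "Complete physical examination and visual acuity assessment". Table 1-1 marks no acuity test at Screening. This does not alter the conclusion, because the trigger in 6.8.2.8 is expressly the Baseline score.

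**What to change.** Reword the recording sentence in 6.8.2.8 along these lines: findings judged to have been present before the first dose, and not to have worsened since, are recorded as medical history; any finding with onset or worsening after the first dose is recorded as an adverse event, with its onset date, under Sections 7.1.1 and 7.2.1. This changes how data are recorded and leaves patient management as it is.

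The cost is one sentence, an onset date on the case report form, and an onset judgement for a few findings, some of which will be uncertain. Separately, reconcile Section 6.2.1 with Table 1-1 on whether acuity is tested at Screening 1.
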